2. INTRODUCTION

There are three basic principles in the management of diabetic foot ulcer (DFU) – adequate debridement and infection control, adequate vascularity, and adequate offloading. Off-loading of the ulcer area is extremely important for the healing of neuropathic plantar ulcers. Total Contact Cast (TCC) remains the gold standard treatment of Diabetic Foot Ulcer (DFU). However, there are many practical problems associated with TCC, including local skin irritation, worsening of deformed toe nails, fungal infections, claustrophobia, joint rigidity, atrophy of the smaller foot muscles, postural instability and painful leg and calf muscles. So, TCCs are underutilized in clinical practice as they are technically difficult and time consuming to apply, relatively expensive and have low patient tolerance. Their use is also contraindicated in patients with infected or ischaemic ulcers. Posterior slab cast (PSC) is also a good offloading modality in neuropathic DFU. It can be more convenient and economical as a single slab can be used till complete healing is achieved. Thus may provide a lesser invasive way of immobilization of the foot in DFU.

3. AIM & OBJECTIVES

Aim of this trial is to compare the efficacy of Posterior slab cast (PSC) with Total Contact cast (TCC) in terms of wound healing and foot related outcomes in patients having neuropathic planter diabetic foot ulcers in a tertiary care diabetic foot clinic.

4. INCLUSION AND EXCLUSION CRITERIA

Inclusion criteria

1. Type 2 Diabetes Mellitus
2. Having solitary neuropathic plantar ulcer
3. Ulcer belonging to Wagner's grade 2 or 3

Exclusion criteria

1. Persons with bilateral DFUs
2. Peripheral vascular disease (ABI < 0.9)
3. Gout
4. steroid intake in the last three months,
5. Stage 4 & 5 chronic kidney disease with estimated glomerular filtration rate (eGFR) <30 ml/min/m²,
6. Bilateral foot involvement,

5. MATERIAL & METHODS

It is an open label randomized control trial. It will be done in ILS Hospital, Kolkata for a trial period of around 3 years.

Diabetic patients attending the foot clinic with plantar ulcer irrespective of age, sex, glycemic control, duration of diabetes, duration of ulcer and presence of infection will be considered for the study. At first patients will be randomly allocated to any one of two off-loading procedures using the randomization table: TCC or PSC. Those who will refuse TCC, will be shifted to PSC group. All patients will be followed up at the foot clinic once in two weeks' basis for device inspection, wound care and wound debridement as and when indicated. After the completion of treatment, all the patients will be followed up to 15 months from the initiation of treatment to identify any recurrence of ulcer.

Two outcome measures will be used. The primary outcome measure is healing of the ulcer after 8 months. The secondary outcome measure is to document which of the device is associated with comparatively better healing at 6 months.

6. OUTLINE OF TIME PLANS:

Proposed date of starting research activity: January 2023

Expected duration of research activity: 1.5 years

Undertaking to provide interim report of the work halfway through it: Yes

Undertaking to provide full report of the work on completion: Yes

7. STATISTICAL ANALYSIS:

Comparison will be done between the two groups. Continuous variables will be compared by t-tests and categorical variables by chi-square test. Baseline comparison will be made using chi-square tests and two-sample t-tests. Continuous variables will be expressed as mean (standard deviation). The differences in pertinent characteristics will be established with the use of t-test for independent samples. A two-sided p value of 0.05 was considered statistically significant.

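### Section 2 calls TCC contraindicated in infected ulcers, yet sections 4 and 5 let infected ulcers be randomised to TCC with no infection rule before allocation or casting

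*Combined protocol and SAP*

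**What the plan says.** Section 2 (Introduction), in explaining why TCC is underused, states: "Their use is also contraindicated in patients with infected or ischaemic ulcers". It states no such contraindication for PSC.

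Section 4 has three inclusion and six exclusion criteria. Exclusion 2 removes peripheral vascular disease, defined as an ABI below 0.9. No exclusion concerns infection. Inclusion criterion 3 reads "Ulcer belonging to Wagner's grade 2 or 3".

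Section 5 (Material & Methods) gives a list of features that do not bear on recruitment, which closes with "duration of ulcer and presence of infection will be considered for the study". It continues: "At first patients will be randomly allocated to any one of two off-loading procedures using the randomization table: TCC or PSC". The only departure from the allocated cast that it describes is "Those who will refuse TCC, will be shifted to PSC group". Two-weekly visits provide "device inspection, wound care and wound debridement as and when indicated".

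The history file in section 12, to be completed at the first outpatient visit, has a yes/no item for INFECTED and a Wagner grade table in which grade 3 is labelled osteomyelitis. Its treatment items include pus for culture, probing, incision and drainage, extensive debridement and surgical referral.

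**The concern.** The plan gives staff two incompatible statements about the same patient. For an infected ulcer allocated to TCC, section 5 leads to the cast and section 2 says the cast should not be used.

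If section 2 is right, following section 5 exposes participants to a risk that the protocol has already recognised. If section 5 is right, a clinician who relies on section 2 may withhold or remove the allocated cast, and nothing says how that patient is then treated. In an open-label trial, such departures would concentrate in infected patients allocated to TCC, which could distort the comparison of healing. Either way, a clinical decision that belongs in the protocol is left to whoever applies the cast.

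**Working it through.** The documents give no sample size, allocation ratio or share of infected ulcers, so there is no figure to reproduce and no exposure to calculate. The check is a comparison of the texts.

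1. **Contraindications carried into eligibility.** Section 2 names two. Ischaemia has a match in section 4 (ABI below 0.9). Infection has none: the six exclusions are bilateral ulcers, peripheral vascular disease, gout, recent steroids, advanced kidney disease and bilateral foot involvement.

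2. **Inclusion criteria.** Type 2 diabetes, a solitary neuropathic plantar ulcer, and Wagner grade 2 or 3. None requires the ulcer to be free of infection. The form's label for grade 3 points towards admitting one kind of infection. It is supporting evidence only, because the form is a general clinic form and the protocol body does not define the grade.

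3. **Recruitment and allocation.** Section 5 disregards infection in recruitment and describes no infection step before the randomisation table is used.

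4. **After allocation.** The one stated exit from TCC is refusal. Infection found at allocation or at a later visit triggers no stated change of device.

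5. **Other provisions on infection.** Section 2 lists infection control among the principles of ulcer management, section 5 provides debridement when indicated, and the form records infection and its treatment. None of these makes allocation or casting conditional on infection being absent or controlled.

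6. **Timing.** Section 6 gives "Proposed date of starting research activity: January 2023" and an expected duration of 1.5 years. January 2023 plus 18 months is about July 2024. Section 5 gives a trial period of around 3 years, and January 2023 plus 36 months is about January 2026. Reference 1 in section 10 was first published on 21 August 2024, so this text was finalised after that date. That is after the end of activity on the first duration and well before it on the second. The actual start is not given. Recruitment status cannot be settled from the documents.

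**The case against.** The strongest reply is that the conflict lies between a background sentence and the operative text. The operative text is consistent: section 5 disregards infection and section 4 admits grade 3. This fits a deliberately inclusive design with an over-broad sentence in the introduction at least as well as it fits a forgotten exclusion. That point stands. It means the repair cannot be presumed to be an exclusion; correcting section 2 is an equal alternative. It does not remove the need to choose, since the sentence is in the protocol and is unqualified.

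A second reply is that being considered for the study refers only to the screening pool. On that reading section 4 would have to remove infected patients, and no criterion does.

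A third is that infection is managed: it is a stated principle, wounds are debrided, and the form covers infection in some detail. This is true and should be credited, but none of it governs who may be cast.

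Two stronger readings are tempting. A reader might infer from the January 2023 start and the August 2024 citation that infected patients are already in TCC. The two stated durations leave that open, and on the shorter one activity would have ended before the citation appeared. A reader might also infer that the risk falls on the TCC arm alone. Section 2 is merely silent about PSC in infected ulcers, and silence does not show that PSC is safe there.

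**Conclusion.** The inconsistency is real and is more than missing detail: a site that follows sections 4 and 5 exactly can cast an infected ulcer in a device that section 2 calls contraindicated. This rests on reading section 2 at face value and on the absence of any infection criterion in sections 4 and 5; it does not depend on how Wagner grade 3 is defined.

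Its size is unknown. The documents do not establish that anyone has been harmed, how many infected patients would be allocated to TCC, which section is clinically correct, or whether recruitment continues. If recruitment is open, the matter should be settled before the next allocation, because it concerns participant safety and a specific, inexpensive rule would resolve it.

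**What to change.** The clinical team should decide which section is right and make one of two changes, not both.

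**(a) If section 2 is right.** In section 5, delete infection from the list of features that do not affect recruitment. In section 4, add an exclusion such as: ulcer infection not controlled at the time of allocation. Define what counts as controlled, and state whether grade 3 with active osteomyelitis is eligible. Apply the rule before randomisation and identically in both arms. The form's INFECTED and Wagner items can serve for this; only the requirement to complete them before allocation is new. Because section 2 stresses off-loading for healing, state that patients who are waiting receive usual clinic off-loading and infection treatment until they become eligible.

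**(b) If TCC is judged acceptable in some infected ulcers.** Correct section 2. State in section 5 which infected ulcers may be cast, with what safeguards, and when the cast must be removed.

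How patients who do not receive or keep their allocated device are analysed is a separate matter for section 7.

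**Cost.** Both routes need changes to the protocol text and probably an ethics amendment, with some delay or loss of recruitment whose size the documents do not allow one to estimate. Route (a) also narrows the population somewhat, more so if active osteomyelitis is excluded, and postpones trial entry for patients whose infection is being treated.

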HDL										
LDL										
VLDL										
LFT										
Bill (T)										
Bill (D)										
Bill (I)										
Protien										
Alb										
Glob										
SGOT										
SGPT										
Alk Ph.										
GGT										
Uric Acid										
HAEMOGRAM										
Hb%										
WBC										
DC										
ESR										
Plat.										
PCV										

Foot Examination :

Foot Examination

Right:

Right :
Left :

ERT :

VII.

Right.

Left : _____

Left :
Hot & C

Hot & Right

Right : _____

Left .

ABT
Right

DIABETES & OBESITY CLINIC

[figure not shown]
DATE	FOLLOW UP COMPLAINTS	TREATMENT ADVICE

NAME: AGE: SEX:

ADDRESS:

MOB.NO: REFERRING DR.:

MEDICAL HISTORY		DIABETIC FOOT HISTORY		
		RT	LT	
Duration of Diabetes		Duration of Ulcer		
Duration of Hypertension		Past H/O Ulcer		
Height		H/O Amputation		
Weight		Joint pain		
BMI		Stiffness		
Dyslipidemia		Dry skin		
SMOKER		Numbness		
CVD		Tingling/Pricking		
CKD		Paresthesia		
Blood Sugar		Claudication		
HbA1C		Cramping		
		Oedema		

[figure not shown]
[figure not shown]

EXAMINATION OF FOOT

INSPECTION

DRY SKIN	YES	NO	ABNORMAL SHAPE	YES	NO
FISSURE	YES	NO	NAIL LESION	YES	NO
DEFORMITY	YES	NO	LOSS OF HAIR	YES	NO
CALLUS	YES	NO			

PALPATION	HOT	COLD	NORMAL
RIGHT			
LEFT			
FOOT PULSES	RT	LT	
DORSALIS PEDIS			
POTERIOR TIBIALIS			
ASSESSMENT OF NEUROPATHY	RIGHT	RIGHT	LEFT
MONOFILAMENT			
VPT			
HCP			

[figure not shown]
[figure not shown]

VASCULAR ASSESSMENT	RIGHT	LEFT
DORSALIS PEDIS		
POSTERIOR TIBIALIS		
BRACHIALIS		
ABI		

RADIOLOGICAL INVESTIGATION (X RAY FOOT)

RT:-

LT:-

DESCRIPTION OF ULCER

Location :-

Size:-

Base:-

Margins:-

Depth:-

CLINICAL DIAGNOSIS			WEGNERS CLASSIFICATION	
	YES	NO	Grade-0	
NEUROPATH Y			1-Superficial Ulcer	
CHARCOT FOOT			2-Deep Ulcer	
PVD			3-Osteomyelitis	
INFECTED			4-Localized Gangrene	
OTHERS			5-Extensive Gangrene	

TREATMENT	YES	NO
Callus and Corn Removed		
Nail paring		
I+D done		
Pus for CS		
Probing		
Extensive debridement		
Surgical Referral		
Others		
OFFLOADING TECHNIQUE	YES	NO
S K OFFLOADING		
OFFLOADING SHOE		
TOTAL CONTACT CAST		
INSTANT TCC		
CUSTOM FOOTWEAR		
OTHERS		

FOLLOW UP

[figure not shown]
Specialised Medical Personnel Curriculum Vitae

Full Name:	[name]
Academic Title:	SENIOR CONSULTANT - DIABETOLOGIST
Present Position:	PRINCIPAL INVESTIGATOR
Business Address:	ILS Hospltd [name]
Relevant Education: (Type of degree and year when awarded)	MBBS-1984, MD-1988

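### Moving patients who refuse TCC into the PSC group after randomisation, and then comparing the two groups, breaks the randomisation and can bias the main result

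*Combined protocol and SAP*

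**What the plan says.** Section 5 (Material & Methods) describes the trial as open label and puts allocation first: "At first patients will be randomly allocated to any one of two off-loading procedures using the randomization table: TCC or PSC". The next sentence deals with refusal: "Those who will refuse TCC, will be shifted to PSC group". The rule runs one way only; nothing is said about patients who decline PSC. The main endpoint is also in section 5: "The primary outcome measure is healing of the ulcer after 8 months".

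Section 7 (Statistical Analysis) says "Comparison will be done between the two groups" and names the tests: "Continuous variables will be compared by t-tests and categorical variables by chi-square test", two-sided at 0.05. It defines no analysis population, no intention-to-treat rule, no sensitivity analysis and no separate reporting of refusers.

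Section 2 (Introduction) makes refusals foreseeable. It describes TCC as "relatively expensive and have low patient tolerance" and lists several discomforts that come with it.

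In section 12 (Copy of History File), the offloading list includes "TOTAL CONTACT CAST", an instant version of it, footwear options and a line for others, but no entry for a posterior slab. The legible part of the form has no field for the randomised arm or for a change of device.

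**The concern.** Randomisation makes the two groups alike in everything except the assigned device. That protection lasts only while patients are counted where they were randomised. Here the patient knows the allocation before refusing, and the refusal rule changes the group to which the patient belongs, which is the unit that section 7 compares.

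Patients who refuse a cast select themselves. They may differ in adherence, ulcer severity or tolerance of immobilisation. Enrolment is open to all ages and to any glycaemic control, ulcer duration and infection status, so prognosis is likely to vary widely. An unadjusted chi-square test on healing cannot separate such differences from a device effect. The trial could report a difference where there is none or hide a real one, and in either case the result would be presented as randomised evidence.

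**Working it through.** **Inputs from the plan.** Open-label allocation before refusal and one-way movement from TCC to PSC (section 5); comparison of two groups by chi-square, two-sided 0.05 (section 7). The plan states no refusal rate, healing rate, sample size or power, so there is no figure of its own to reproduce. Everything numerical below is an assumption, shown over a range.

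**Set-up.** Suppose the devices heal equally well. Let r be the share of patients who would refuse TCC, a the healing rate in acceptors and b the healing rate in refusers, with equal numbers randomised to each arm.

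- TCC group after the move (acceptors only): a.
- PSC group after the move (its own mixture plus the TCC refusers): [(1 − r)a + 2rb] / (1 + r).
- False difference, TCC minus PSC: 2r(a − b) / (1 + r).
- Difference when analysed by randomised arm: 0, because both arms have the mixture (1 − r)a + rb.

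**Worked case.** With a = 0.85, b = 0.65 and r = 0.20, the PSC group heals at (0.80 × 0.85 + 0.40 × 0.65) / 1.20 = (0.68 + 0.26) / 1.20 = 0.783. The false difference is 0.850 − 0.783 = 0.067. The formula gives the same: 0.40 × 0.20 / 1.20 = 0.067.

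**Range.** The false-positive rates come from simulation of the uncorrected chi-square test under no device effect, with a = 85%. They are approximate, and n is the number randomised per arm.

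| Gap a − b | Refusal r | False difference (points) | False positives, n = 50 | False positives, n = 100 |
|---|---|---|---|---|
| 10 points | 10% | 1.8 | 5% | 6% |
| 10 points | 20% | 3.3 | 7% | 9% |
| 10 points | 30% | 4.6 | 8% | 12% |
| 20 points | 10% | 3.6 | 7% | 10% |
| 20 points | 20% | 6.7 | 12% | 21% |
| 20 points | 30% | 9.2 | 18% | 33% |
| 30 points | 10% | 5.5 | 10% | 17% |
| 30 points | 20% | 10.0 | 22% | 40% |
| 30 points | 30% | 13.8 | 33% | 61% |

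Analysed by randomised arm, the false-positive rate stays at about 5% throughout.

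**Direction.** With a = 60%, b = 80% and r = 20%, the false difference is −6.7 points (in favour of PSC), with about 16% false positives at n = 100. With a = b = 70% there is no false difference and the rate stays near 5%.

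**Group sizes.** A 50:50 split becomes 45:55, 40:60 or 35:65 at r = 10%, 20% or 30%.

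**The case against.** Five points can be made for the plan or against the size of the claim.

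- **The plan never literally says that refusers are analysed in PSC.** The sentence might describe only the device they receive. That is possible, but the words move the patient to a group, section 7 compares groups, and no as-randomised rule appears anywhere. If the sponsor means otherwise, the text has to say so.
- **Bias needs refusal to be related to healing.** This stands. The accurate statement is that the rule can bias the result, by an amount and in a direction that the plan's figures cannot settle.
- **The inflation can be small.** This stands for small gaps and small trials. A continuity-corrected chi-square, which the plan neither specifies nor excludes, would lower the rates further: for the 20-point gap at 50 per arm, to about 4%, 7% and 11%. The correction makes the test more conservative but leaves the false difference in the estimate unchanged.
- **The form is weak evidence.** A slab could be entered under the line for others, the form is headed for the first visit, and some of its figures are not shown. This stands. The form is a secondary matter, and the conclusion does not depend on it.
- **Analysis by randomised arm has a price.** If refusers wear PSC but count as TCC, a true difference D among acceptors shrinks to (1 − r)D. Holding power then takes roughly 1/(1 − r)² times as many patients: 1.23, 1.56 or 2.04 times at r = 10%, 20% or 30%. This stands and must be planned for. Dilution also pulls towards no difference, so a null result should not by itself be read as showing that PSC performs as well as TCC.

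**Conclusion.** The concern holds, and the text must be changed before the analysis. Followed as written, the plan replaces the randomised comparison with a partly self-selected one for its primary outcome. Over refusal of 10% to 30% and healing gaps of 10 to 30 points, the false difference runs from 1.8 to 13.8 percentage points. The false-positive rate of the nominal 5% test runs from about 5% to 33% at 50 per arm and from about 6% to 61% at 100 per arm. These figures rest on assumed refusal rates, healing rates and sample sizes, on no true device effect and on an uncorrected chi-square test. The structural fault does not rest on them: once refusers have changed group, a device effect cannot be told apart from a difference between acceptors and refusers.

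**What to change.** 1. In section 7, state that the primary comparison of healing counts every patient in the arm to which he or she was randomised, whatever device was worn, and that an as-treated comparison is supportive only. Apply the same rule to patients who decline PSC. In section 5, reword the refusal sentence so that it describes a change of device, not of analysis group. This leaves the plan's existing provision for refusers as it is.
2. Report the number of refusals in each arm, with reasons.
3. Record for every patient the randomised arm, the device actually worn, and the date of and reason for any switch. Add an entry for posterior slab cast to the offloading list.
4. Consider asking, before randomisation, whether the patient would accept either device. Randomise only those who would, and follow the others outside the randomised comparison. Item 1 is enough to restore a valid test; this step limits the dilution.

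The cost is a few sentences and a few form fields. The willingness check narrows enrolment somewhat. Analysis by randomised arm dilutes the device contrast, so when a sample size is set it should allow for the expected refusal rate, using the factor 1/(1 − r)².

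### If recurrence to month 15 is compared by the plan's chi-square rule, unequal time since healing biases the crude proportion, mostly by a small amount, against a faster-healing device

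*Combined protocol and SAP*

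**What the plan says.** Section 3 sets the aim as comparing the two casts "in terms of wound healing and foot related outcomes"; the foot-related outcomes are not itemised.

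Section 5 fixes the length of follow-up: "all the patients will be followed up to 15 months from the initiation of treatment to identify any recurrence of ulcer". The clock starts when treatment starts, not when the ulcer heals. The same section then closes the list of outcomes: "Two outcome measures will be used". The first is stated as "The primary outcome measure is healing of the ulcer after 8 months". The second concerns healing at 6 months. Neither is recurrence.

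Section 7 is general: "Comparison will be done between the two groups", and "Continuous variables will be compared by t-tests and categorical variables by chi-square test". The two-sided significance level is 0.05. No time-to-event or person-time method is named.

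**The concern.** Patients stay in follow-up to month 15 for the stated purpose of finding recurrence, so the report will probably show recurrence by arm. The only tool the plan offers for a yes/no variable is a chi-square test on counts. That test treats every healed patient as equally observed, and they are not. A patient healed at month 2 is watched for 13 months, and one healed at month 4 for 11 months.

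If one device heals faster, its healed patients have longer to recur, and the crude proportion is higher for that reason alone. The trial could then report that a device heals faster but recurs more when recurrence after healing is the same. It could also hide part of a real reduction in recurrence.

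**Working it through.** **Inputs from the documents.** Month 15 from the start of treatment (section 5), months 8 and 6 for healing (section 5), chi-square and two-sided 0.05 (section 7). The plan states no recurrence figure to reproduce.

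**Assumed inputs, because the documents give none.** Healing time H is exponential with rate r = ln 2 / median. Recurrence after healing has a constant hazard λ, the same in both arms, of 1-5% per month. There is no loss to follow-up. Healing is counted up to month K. The plan does not say which K would apply to a recurrence denominator, so both 8 (the primary horizon) and 15 are shown.

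**Formulas.**
- Healed share: P(H<K) = 1 − exp(−rK).
- Healed by K and recurred by month 15: P(H<K) − r·exp(−15λ)·[1 − exp(−(r−λ)K)]/(r−λ).
- Crude proportion among healed: the second divided by the first.

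**Worked case: λ = 0.03, K = 15, medians 2 v 4 months.**
- Median 2 (r = 0.34657): 0.99448 − 0.69201 = 0.30247; divided by 0.99448, this is 30.4%.
- Median 4 (r = 0.17329): 0.92567 − 0.68124 = 0.24443; divided by 0.92567, this is 26.4%.
- Gap: 4.0 points, with identical hazards. The mean time from healing to month 15 is 12.20 v 10.43 months.

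**Crude recurrence among healed patients at λ = 0.03, with the gap in points and, in brackets, its range over λ = 0.01-0.05:**

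| Medians (months) | Healed by month 8 | Gap | Healed by month 15 | Gap |
|---|---|---|---|---|
| 2 v 3 | 31.5% v 30.4% | 1.02 (0.43-1.35) | 30.4% v 28.1% | 2.35 (0.95-3.25) |
| 2 v 4 | 31.5% v 29.9% | 1.60 (0.67-2.12) | 30.4% v 26.4% | 4.01 (1.61-5.58) |
| 3 v 6 | 30.4% v 29.2% | 1.20 (0.50-1.59) | 28.1% v 24.4% | 3.68 (1.46-5.20) |
| 3 v 4 | 30.4% v 29.9% | 0.58 (0.24-0.77) | 28.1% v 26.4% | 1.66 (0.66-2.33) |

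The gap is zero when the medians are equal.

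**False-positive rate of chi-square at 0.05** (first three median pairs, λ = 0.03-0.05). The plan states no sample size, so three are assumed.

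| Per arm | Month-8 counting | Month-15 counting |
|---|---|---|
| 30 | about 5-6% | about 5.5-7.6% |
| 50 | about 5-6% | about 5.6-8.8% |
| 100 | about 5-6% | about 6.4-12% |

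Log-rank timed from healing stayed at 4.6-5.4% in simulation at 100 per arm. The rate per person-month returns 0.030 in every arm for both values of K when λ = 0.03.

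**Masking.** Suppose the faster device truly has a 20% lower hazard (0.024 v 0.030).
- Month-15 counting: 25.2% v 30.4% (5.2 points) if both medians are 2 months, but 25.2% v 26.4% (1.2 points) with medians 2 v 4.
- Month-8 counting: 26.1% v 31.5% (5.4 points) falls to 26.1% v 29.9% (3.8 points).

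**The case against.** The strongest objection is that the bias belongs to an analysis the plan does not state. Section 5 says recurrence will be identified, not tested, and its list of two outcomes reads as complete. The chi-square sentence is generic, and the foot-related outcomes in section 3 need not include recurrence. This stands: the point is conditional on a crude comparison being made.

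The second objection is size, and it also stands in large part. Under month-8 counting the test is close to its nominal level at every sample size tried. Noticeable inflation needs month-15 counting, a large difference in healing speed and a fairly large trial, none of which the documents state.

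A reader might infer more than the documents support:
- **That the main results are biased.** They are not. Both declared outcomes are healing at fixed times.
- **That the gap with all randomised patients as denominator is further bias.** For the first three median pairs that gap is 1.5-11.8 points (month 8) or 1.2-10.4 points (month 15). It is a true difference in the chance of healing and then recurring, and misleads only if read as one device causing more recurrence.
- **That healing and recurrence dates will not be recorded.** The case report form in section 12 has a dated follow-up sheet and follow-up figures that are not shown, so this cannot be concluded.

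The lack of a recurrence definition and of a visit interval after treatment is missing detail, and the point does not rest on it.

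**Conclusion.** The point holds in conditional form. The direction follows from the plan's own clock: with a fixed end at month 15 counted from treatment, earlier healing means longer time at risk. The size rests wholly on assumed healing times, a constant and equal recurrence hazard and complete follow-up. Under these, the spurious gap among healed patients is 0.4-2.1 points with healing counted to month 8 and 0.9-5.6 points with healing counted to month 15. For the milder contrast of 3 v 4 months it is 0.2-2.3 points across both rules. Healed patients are not a randomised group, so differences in case mix could add to the bias or offset it. Priority is low to moderate: it concerns an undeclared outcome, but the better method is simple and should be fixed before the data are seen.

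**What to change.** 1. Declare recurrence as an exploratory or secondary outcome, with a definition and the month up to which healing counts.
2. Instead of chi-square on raw counts, analyse time from healing to recurrence among healed patients (Kaplan-Meier with log-rank, or rate per person-month), censored at month 15 or last visit. Label it descriptive, because the healed subset is formed after randomisation.
3. Beside it, report one summary for all randomised patients by assigned arm, such as the proportion healed and ulcer-free at month 15, or ulcer-free months to month 15 (zero if never healed). Under the model above at 3% per month, ulcer-free months would be 10.1 v 9.1, 10.1 v 8.1 and 9.1 v 6.7 for the first three median pairs, so this summary credits faster healing.

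The cost is a few sentences of analysis text, plus making sure that a healing date and a recurrence date are captured for each patient. There are two downsides. Dates are known only to the nearest visit, so visits after healing should be equally spaced in both arms. The all-randomised summary also needs a stated rule for patients lost before month 15.

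### The aim includes foot related outcomes, but both declared outcomes are ulcer healing; recurrence is followed without being declared, and no complication, tolerability or refusal outcome is planned

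*Combined protocol and SAP*

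**What the plan says.** Section 3 (Aim & Objectives) sets out to compare the efficacy of the posterior slab cast (PSC) with TCC "in terms of wound healing and foot related outcomes in patients having neuropathic planter diabetic foot ulcers". The available text does not say which foot outcomes are meant.

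Section 5 (Material & Methods) fixes the outcomes: "Two outcome measures will be used. The primary outcome measure is healing of the ulcer after 8 months". It continues: "The secondary outcome measure is to document which of the device is associated with comparatively better healing at 6 months". Just before this list, it plans that after treatment "all the patients will be followed up to 15 months from the initiation of treatment to identify any recurrence of ulcer". On treatment, "All patients will be followed up at the foot clinic once in two weeks' basis for device inspection, wound care and wound debridement". Patients who refuse TCC are moved to the PSC group.

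Section 2 (Introduction) argues that TCC is underused. It lists practical problems "including local skin irritation, worsening of deformed toe nails, fungal infections, claustrophobia, joint rigidity, atrophy of the smaller foot muscles, postural instability", and adds leg and calf pain. It also calls TCCs "technically difficult and time consuming to apply, relatively expensive and have low patient tolerance", and presents PSC as more convenient, cheaper and less invasive.

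Section 7 (Statistical Analysis) gives general rules, with chi-square tests for categorical and t-tests for continuous variables. It names no outcome. In section 12, the case report form is headed for the first outpatient visit, and a dated follow-up sheet has columns for complaints and treatment advice.

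**The concern.** The aim names two domains and the outcome list serves one. The secondary outcome is an earlier reading of the primary and adds no new domain. Much of the introduction's argument for PSC is that TCC is hard on the patient, yet the plan declares no outcome that measures this in either arm.

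This matters most if healing turns out similar. The choice between devices would then turn on burden, complications and acceptance, and the trial would have no prespecified comparison of any of them. A new skin lesion under the device, or a new foot infection, in a patient whose index ulcer still heals by month 8 would appear in the declared outcomes only as a success. Refusal of TCC, the most direct sign of poor tolerance, would be handled as a change of group and not reported as a result.

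**Working it through.** The documents give no sample size, healing rate or complication rate, so there is no planned figure to reproduce. The check sets the sections side by side.

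1. **Declared outcomes (section 5).** There are two: healing after 8 months and healing at 6 months. Healing: 2 of 2. Non-healing foot outcome, complication, tolerability or refusal: 0 of 2.

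2. **Problems attributed to TCC (section 2).** Skin irritation, worsening of deformed nails, fungal infection, claustrophobia, joint rigidity, small-muscle atrophy, postural instability, and leg and calf pain make eight. Matched by a declared outcome: 0 of 8.

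3. **Foot outcomes collected but undeclared (section 5).** There is one, recurrence to month 15. It has no definition (same site or any site, and how it is confirmed), no denominator and no analysis of its own. The denominator is not a formality:
   - Only a healed ulcer can recur, so a proportion among healed patients compares subsets formed after randomisation.
   - The time at risk depends on when healing occurs. A patient healed at month 6 is observed for 15 − 6 = 9 months, and one healed at month 8 for 15 − 8 = 7 months. If one device heals faster, its patients also have longer in which to recur.

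4. **Opportunity to record complications (section 5).** With two-weekly visits, 8 months × 52/12 = 34.7 weeks, and 34.7 / 2 is about 17 inspections for a patient still in treatment. The visits exist. What is missing is a uniform item to record at them.

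5. **Forms (section 12).** Nail lesion, joint pain, stiffness and cramping are on the examination and history forms, but nothing in the plan calls for repeating them. The follow-up sheet takes complaints as free text. In an open-label trial, what is written there depends on what is asked and volunteered, which may differ between arms.

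6. **Groups for comparison (section 5).** TCC refusers are moved to PSC, and the text does not say in which arm they are counted. If they are counted under PSC, the patients least willing to accept TCC leave the TCC group and any tolerability comparison is distorted.

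**The case against.** The strongest reply is that the plan collects more than its outcome list suggests. Much of that reply stands, and it limits what can be concluded.

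- A reader might infer that the trial can report healing only and cannot answer half of its aim. The documents do not support that: recurrence is a foot outcome, and follow-up for it is planned in all patients. Section 7's general chi-square rule could also be applied to it. What remains is that it is not declared or defined.
- A reader might infer that the two-weekly inspections feed no outcome. They include wound care and are the only on-treatment visits described, so they are the natural place to observe healing.
- A reader might infer that harm cannot be seen at all. The complaints column can capture some of it. Some figures of the forms are not shown, so the absence of a structured follow-up form cannot be confirmed.
- A reader might infer that the aim promises a tolerability or safety comparison. It speaks of efficacy, so that gap is against the introduction, not the aim. The introduction also argues from technical difficulty, time, cost, contraindications and convenience, so side effects are a main part of the rationale but not all of it.

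Against a complication outcome, it can fairly be said that a single composite mixes amputation with nail changes, and minor events could dominate it. That is a reason to report components separately, not to leave them unrecorded.

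**Conclusion.** The point holds in this limited form. Of two declared outcomes, both are healing. The second domain of the aim has no defined outcome. The one non-healing foot outcome that is followed, recurrence, is undeclared. No complication, tolerability or refusal comparison is prespecified, although these carry much of the case for PSC.

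The primary healing comparison is not affected by this gap, so it is a point that should be corrected and not one that invalidates the design. Its effect on precision cannot be quantified, because the documents give no sample size or event rates. The conclusion rests on reading the outcome list in section 5 as complete, which its wording supports, and on the forms as far as they are visible.

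**What to change.** In section 5, replace the closed list of two with the existing healing outcomes plus three secondary outcomes. Compare all of them by arm as randomised, with TCC refusers counted in the TCC arm:

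1. Ulcer recurrence to month 15, with a definition and a stated denominator. If the denominator is healed patients, also give the result over all randomised patients.
2. The proportion with at least one device-related or foot complication to month 8, with each component also reported separately: new ulcer or skin breakdown under the device, nail or fungal worsening, foot infection new relative to baseline, amputation, and fall. The baseline reference is needed because section 5 takes patients whether or not infection is present.
3. The proportion who refused or stopped the assigned device, recorded in both arms.

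Record items 2 and 3 on the same short yes/no checklist in both arms at the existing two-weekly inspections. The list does not cover every problem in the introduction (claustrophobia and muscle atrophy, for example), so claims should stay within what is recorded.

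The cost is a few sentences, a short form and a few minutes per visit, with no extra visits, staff or procedures. The complication and refusal data will be open-label and supportive only.

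If the sponsor will not add these, narrow the aim in section 3 to healing and recurrence, and draw no conclusion on tolerability or safety.
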